8.4 Inclusion and exclusion criteria

Inclusion criteria: 1. Patients admitted to the Centro Medico ISSEMYM Toluca Arturo Montiel Rojas, diagnosed with COVID-19. 2. Patients in need of supplemental O₂ with nasal prongs or mask-reservoir due to satO₂ <90% and respiratory distress. 3. With concomitant diseases such as cardiovascular disease, diabetes mellitus 2, hypertension, overweight or obesity BMI <35. 4. 5. Over 30 years of age. 6. Tolerant of oral feeding. 7. Signed informed consent letter.

Non-inclusion criteria: 1. Who requires mechanical ventilatory support. 2. 2. Present neurological or neurodevelopmental disorders. Severe gastroesophageal reflux and/or dysphagia. 4. 4. Patients with any type of surgery performed in a period of less than 3 months. 5. Allergies to any ingredient of the study treatment. 6. Who present acute malnutrition. 7. Patients who require admission to the Intensive Care Unit. 8. Who has criteria of sepsis or septic shock. 9. Glomerular filtration rate less than 60ml/min/1.73m².

Criteria for elimination: 1. Treatment failure. 2. Admission to ICU for any reason. 3. Patients who do not tolerate the oral route. 4. Reactions to treatment that compromise the health of the patients.

Sampling and allocation: Consecutive cases. Systematic randomized allocation by means of a sequence of random numbers constructed with the Excel program divided into two groups.

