8.4 Procedure

Once the participants have been selected, the patients and/or family members will be interviewed to explain the protocol and to obtain the signatures of the informed consent letters (Annex 1). Confirmatory test for COVID-19 by PCR, which should confirm the diagnosis in order for the study to continue. Complete clinical and dietary history. Complete blood count: leukocytes, neutrophils, eosinophils, basophils, lymphocytes, monocytes, erythrocytes, red blood cell count, hemoglobin, hematocrit, mean corpuscular volume (MCV), mean hemoglobin concentration (MHC), mean corpuscular hemoglobin concentration (MCHC), platelets and mean platelet volume (MPV). 4. Blood chemistry (glucose, urea, urea nitrogen (BUN), creatinine, BUN/creatinine ratio, uric acid, calcium, phosphorus, sodium, potassium, chloride, magnesium, glomerular filtration rate (GFR), triglycerides, total cholesterol, low density lipoproteins (LDL), high density lipoprotein (HDL), very low density lipoprotein (VLDL), total lipids, total, direct and indirect bilirubin, alanine aminotransferase (ALT), aspartate aminotransferase (AST), gamma glutamyl transpeptidase (GGT), lactate dehydrogenase (LDH), total proteins and albumin. 5. D-dimer (see section 2.3.6). 6.

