2. To evaluate the effect of NSS on clinical and biochemical changes among patients.
3. To evaluate the effect of NSS on the biochemical status associated with overall mortality.

Study hypotheses

The null hypothesis: The nutritional support system will not reduce mortality or increase survival in patients with COVID-19 in stage III and comorbidities compared to conventional nutritional therapy.

Research hypothesis: The nutritional support system will reduce mortality and increase survival in patients with COVID-19 in stage III and comorbidities compared to conventional nutritional treatment.

Section 3: Trial Methods

9. Trial design - description of trial design

Item 9: Brief description of trial design including type of trial

Randomized, blinded, controlled clinical trial. Selected patients will be randomized into two groups: 1) Control Group (CG) will receive the hospital diet and 2) Intervention Group (IG) will receive the hospital diet and the NSS. Treatment allocation will have a 1:1 ratio.

10. Randomization

Randomization will be performed using a raffle; eighty numbers are to be placed (from 1 to 80). Subsequently, each number will be randomly selected from the raffle and sequentially assigned to one of the two groups, until reaching 40 numbers per group. Each number represents the moment the patient enrolls. In this way, once the recruitment starts, the first patient will be assigned number one; the second will be number two, and so on.

11. Sample size

Item 11: Full details of the same size calculation or alternatively reference to sample size calculation in protocol (instead of replication in SAP).

The sample size will be calculated using the formula: $n = \frac{z^2 p q}{e^2}$, where: 95% confidence level ($z = 1.96$), $p = 0.975$, $q = 0.025$, with a margin of error of 5% ($e = 0.05$), obtaining 38 patients per group for the sample.

12. Framework

Item 12: Superiority, equivalence or non-inferiority trial hypothesis testing framework, and wick comparisons will be presented on this basis.

The effect of NSS in increasing survival and reducing mortality in patients with COVID-19 will be demonstrated by the significant superiority of IG over CG.

13. Statistical Interim analyses and stopping guidance

Item 13a: Information on interim analyses specifying what interim analyses will be carried out and listing of time points:

No interim analyses are planned in the study.

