- SpO2 without supplemental oxygen, use of home oxygen upon hospital discharge, days of supplemental oxygen use, post-covid syndrome, decrease in body weight: all will be analyzed from hospital discharge until day 40.

Section 4: Statistical Principles

16. Confidence intervals and p-values

Item 16: Level of statistical significance

P values ≤ 0.05 will be considered indicative of statistical significance in all cases. P values will be one-sided.

Item 17: Description of any planned adjustment for multiplicity, and if so, including how the type I error is to be controlled

This study will not analyze data that required multiplicity tests. To avoid type 1 error, an alpha value of 5% will be used (considering $p < 0.05$ significant), aberrant data will be eliminated, validated tests applicable to the study variables will be defined and established, specific inclusion criteria will be implemented for homogenization of the sample to avoid bias variables, and a specific sample size calculation will be performed.

Item 18: Confidence intervals (CI) to be reported

All the confidence intervals presented will be 95%.

19. Adherence and Protocol Deviations

Item 19a: Definition of adherence to the intervention and how this is assessed including extent of exposure.

The intervention will consist of: 1) 2 envelopes of NSS taken in a period of less than 15 minutes (without the presence of vomiting) after morning and afternoon meals during the first 21 days or until hospital discharge, 2) 1 capsule of *Saccharomyces Boulardii* before the NSS and 1 capsule with the second envelope for 6 days or until hospital discharge, 3) intramuscular B complex; 1 ampoule after meals for 5 days or at hospital discharge.

Adherence to treatment will be established as taking more than 95% of the NSS and not fasting for 2 consecutive days.

Item 19b: Description of how adherence to the intervention will be presented

The intervention will be applied by the research team, who will be responsible for the application and collection of data, which will be reported in daily formats in the morning and afternoon shifts.

The clinical investigators are going to prepare each supplement, administer, and witness each intake of the NSS, registering the time as well as any immediate side effects such as vomiting, bloating, and abdominal pain.

Item 19c: Definition of protocol deviation for the trial:

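### Neither document provides for concealing the pre-drawn allocation list, and the SAP and protocol describe different ways of making it, so selection bias at enrolment is possible

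*SAP*

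**What the plan says.** SAP section 9 describes the design: "Randomized, blinded, controlled clinical trial", and "Treatment allocation will have a 1:1 ratio". Under SAP section 10, numbers 1 to 80 go into a raffle, and "each number will be randomly selected from the raffle and sequentially assigned to one of the two groups, until reaching 40 numbers per group". The numbers are then tied to enrolment order: "Each number represents the moment the patient enrolls. In this way, once the recruitment starts, the first patient will be assigned number one".

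Protocol 8.4 (sampling and allocation) gives another method: "Systematic randomized allocation by means of a sequence of random numbers constructed with the Excel program divided into two groups". In the protocol's procedure section, assignment is step 12, after consent, PCR and baseline measurements.

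Neither document names who generates or keeps the sequence, says that it is kept from those who enrol, or describes a release step. The only envelopes mentioned, in SAP Item 19a, are supplement sachets. SAP Item 25a leaves the details of randomisation to the manuscript.

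On delivery, SAP Item 19b says: "The clinical investigators are going to prepare each supplement, administer, and witness each intake of the NSS". The control group receives the hospital diet, and no placebo is described.

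**The concern.** Randomisation protects the survival comparison only if the person deciding whether and when to enrol a patient cannot foresee the arm. Under SAP section 10 the whole sequence exists before recruitment, so the protection depends entirely on how the list is kept and released, and the plan says nothing on either.

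There is room for selective enrolment. Several entry criteria in protocol 8.4 call for clinical judgement: respiratory distress, tolerance of oral feeding, need for intensive care, signs of sepsis. If the next arm were known, a sicker patient could be deferred or declined without breaking any written rule.

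The word blinded in the design label does not answer this. Concealment acts before assignment and blinding after it. Here the investigators who give the supplement also know the past allocations.

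The stakes are high because few events carry the conclusion. The SAP's Figure 2 legend reports 7 deaths of 40 in the control group (CG) and 1 of 40 in the intervention group (IG).

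**Working it through.** **1. The two allocation texts side by side**

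| Item | SAP section 10 | Protocol 8.4 |
|---|---|---|
| Tool | Raffle of numbers 1 to 80 | Excel random-number sequence, called systematic |
| Restriction | 40 per arm | Two groups, no count given |
| Link to patient | Order of enrolment | Not stated |
| Who generates and holds the list | Not stated | Not stated |
| Concealment and release | Not stated | Not stated |

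The methods differ, and neither includes concealment.

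**2. How much concealment would protect**

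- If an enroller could see the list, 80 of 80 allocations would be foreseeable. This is a conditional statement, not an estimate of what happened.
- If the list is concealed but past arms are known, the best strategy is to guess the arm with more places left. For one block of 80 split 40/40, the expected number of correct guesses is 40 + (4^40 / C(80,40) − 1)/2 = 40 + (11.245 − 1)/2 = 45.1, or 56.4% against 50% by chance. The expected number of allocations at the end that are certain is 80/41 = 1.95.

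Concealment therefore removes most of the exposure. Small blocks of known size would not help: the same calculation gives 70.8% for blocks of 4.

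**3. How far the result depends on single patients**

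Inputs: 40 per arm and deaths 7 v 1 (Figure 2 legend); log-rank test (SAP section 27); one-sided p at 0.05 (SAP Item 16). Death times are not tabulated, so I took every possible order of the deaths, assuming no ties and no censoring before the last death. With a CG and b IG patients at risk at each death, E = Σ a/(a+b), V = Σ ab/(a+b)², and z = (O − E)/√V, where O is the number of CG deaths. The extremes are IG deaths last and IG deaths first.

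| Deaths CG v IG | IG deaths last | IG deaths first | One-sided p | Two-sided p |
|---|---|---|---|---|
| 7 v 1 | (7 − 3.813)/√1.994 = 2.257 | (7 − 3.905)/√1.997 = 2.190 | 0.012-0.014 | 0.024-0.029 |
| 6 v 1 | (6 − 3.361)/√1.746 = 1.997 | (6 − 3.440)/√1.749 = 1.936 | 0.023-0.026 | 0.046-0.053 |
| 6 v 2 | (6 − 3.827)/√1.995 = 1.539 | (6 − 3.985)/√1.999 = 1.425 | 0.062-0.077 | 0.124-0.154 |

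The reported log-rank p of 0.027 lies inside the two-sided range at 7 v 1, so the approach reproduces the document's own figure to that extent.

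The 6 v 1 row represents one control patient who died being replaced by one who survived. The 6 v 2 row represents one death falling in the other arm. At one-sided 0.05, the first leaves the result significant and the second does not. On a two-sided reading, 6 v 1 straddles 0.05.

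**The case against.** The strongest reply is that a sequence fixed before recruitment and used in order is ordinary practice, that silence about who held it is a reporting gap, and that SAP Item 25a promises the details later. The first part stands: the pre-drawn list is not itself a fault. The rest does not close the point. A plan that can be followed to the letter with the list in anyone's hands gives no protection, and a promise to describe the method afterwards does not specify one.

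Four stronger readings are tempting and are not supported:

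- **The list was open.** The documents are silent on access. They do not say that any enroller saw it.
- **The team that gives the supplement also enrols.** SAP Item 19b covers preparation, administration and data collection. No text says who screens or obtains consent.
- **Patients were given an arm before eligibility was known.** Protocol 8.4 requires a PCR result ("Confirmatory test for COVID-19 by PCR, which should confirm the diagnosis in order for the study to continue") and lists it ahead of assignment. SAP section 9 says that it is selected patients who are randomised, and the CONSORT list in Item 23 puts eligibility, including the laboratory criteria, before randomisation. Linking the number to enrolment fixes order; it does not place enrolment ahead of the tests.
- **Deferring one sick control patient would overturn the result.** Fisher's exact test suggests this (one-sided 0.028 at 7 v 1, 0.054 at 6 v 1), but the planned test is the log-rank, on which 6 v 1 stays below one-sided 0.05.

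The baseline tables settle nothing either way. Cardiovascular disease is more frequent in the control group (17 v 10), while qSOFA is higher in the intervention group (0.65 v 0.425).

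**Conclusion.** The point holds as a gap in the plan: arms are tied to enrolment numbers before recruitment, the two documents disagree on how the sequence is made, and neither conceals it or controls its release. Selection bias is possible; it is not shown, and a reader should not infer that it occurred.

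The exposure matters because the survival conclusion rests on 8 deaths. One death in the other arm takes the planned test from one-sided p of 0.012-0.014 to 0.062-0.077. One fewer control death takes it only to 0.023-0.026. These ranges assume 40 per arm, no ties and no censoring before the last death. They show how sensitive the result is and do not estimate any bias.

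**What to change.** Replace SAP section 10 and the protocol's allocation sentence with one method. The sequence is generated once and kept in sequentially numbered, opaque, sealed envelopes by an existing team member who neither screens nor obtains consent. Each envelope is opened only after consent and eligibility have been recorded with date and time. The cost is eighty envelopes, a log and a revised paragraph in each document, with no extra patients or procedures.

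The Figure 2 legend reports follow-up from September 2020 to April 2021, so for this trial the applicable form is disclosure:

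- State which method was used, raffle or Excel sequence, who generated and held the list, and how each allocation was released.
- If there was no concealment, say so and qualify the survival conclusion accordingly.
- Add dates to the screening counts already planned under SAP Items 21 to 23, and show patients who were eligible but not enrolled.

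The cost is a short text change, dates taken from the screening records, and possibly a less favourable description of the design.

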Categorical data will be summarized by numbers and percentages. Normality tests will be applied to evaluate the distribution of the data. If the continuous data present a normal distribution, they will be assumed by mean, SD, and range. If they do not present a normal distribution, they will be summarized with the median and the IQR. Minimum and maximum values will also be presented for continuous data. Statistical significance tests will be performed between both groups in the baseline to rule out significant differences.

Section 6: Analysis

26. Outcomes definitions

Item 26a: Specification of outcomes and timings

Primary outcomes

- Overall mortality and survival will be assessed from the baseline to day 40.
- Progression to AVM will be assessed from baseline until the last patient is intubated.
- Mortality and survival in intubated patients will be assessed from baseline to day 40.

These results will be included in the results section of the manuscript.

Secondary Outcomes

Administration of supplemental oxygen flow, oxygen saturation (spO₂), qSOFA scale, and gastrointestinal function will be assessed by comparing at baseline to day 3 intragroup and intergroup. The PHQ-9 test will be assessed at baseline and at discharge between both groups.

These results will be included in the secondary outcomes section of the manuscript. Analysis of the association of baseline biochemical parameters and mortality will be considered in a table and in the secondary outcomes section of the manuscript.

The spO₂ without supplemental oxygen requirement, home supplemental oxygen requirement, post COVID syndrome, and body weight at day 40 will be analyzed between both groups in a table.

These results are included in the follow-up section of the manuscript.

Item 26b: Specific measurement and units

- SpO₂ (%)
- Mortality (days of death)
- Kilocalories (kcal / day)
- PHQ9 (pts).
- Temperature (°C).
- Hemoglobin (g / dL).
- Mean corpuscular volume (fL).
- Mean corpuscular hemoglobin concentration (g / dL).
- Leukocytes ($10^3 / \mu\text{L}$).
- Neutrophils (%).
- Platelets ($10^3 / \mu\text{L}$).
- Glucose (mg / dL).
- Total cholesterol (mg / dL).
- Triglycerides (mg / dL).
- Aspartate aminotransferase (U / L).
- Alanine aminotransferase (U / L).
- Albumin (g/dL).
- Blood Urea Nitrogen (mg / dL).
- Urea (mg / dL).
- Creatinine (mg / dL).
- Glomerular filtration rate
- Ferritin (ng / mL)
- Fibrinogen (mg / dL)
- C-reactive protein (mg / L)
- Dimer-D (ng / mL)

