- Procalcitonin (ng / mL)

27. Analysis methods

To consider statistical significance in the results, a value of $p < 0.05$ will be used.

The analysis of the primary and secondary outcomes is shown in the following table.

Variable	Outcome	Timing	Normality test	Summary results	Parametric test	Nonparametric test	Categorical data test	Analysis type
Overall survival	Primary	40 days follow-up	-	Kaplan-Meier	-	-	Log Rank	Intergruppal
Progression to intubation	Primary	until the last patient is intubated	-	Kaplan-Meier	-	-	Log Rank	Intergruppal
Survival in intubated	Primary	40 days follow-up	-	Kaplan-Meier	-	-	Log Rank	Intergruppal
Oxygen flow (L)	Secondary	Basal vs day 3	Shapiro-Wilk	Mean and SD	Paired T test	Wilcoxon	-	Intragruppal
qSOFA (pts)	Secondary	Basal vs day 3	Shapiro-Wilk	Mean and SD	Paired T test	Wilcoxon	-	Intragruppal
Defecations per day (No.)	Secondary	Day 3	Shapiro-Wilk	Mean and SD	Unpaired T test	Mann Whitney	-	Intergruppal
Distension (Yes/No)	Secondary	Day 3	Shapiro-Wilk	Proportions	-	-	Fisher	Intergruppal
PHQ-9 (pts)	Secondary	Basal vs Discharge	Shapiro-Wilk	Mean and SD	Paired T test	Wilcoxon	-	Intragruppal
Oxygen saturation >90%	Secondary	Day 3	Shapiro-Wilk	Proportion	-	-	Fisher	Intergruppal
Hydric balance	Secondary	Day 3	Shapiro-Wilk	Mean and SD	Unpaired T test	Mann Whitney	-	Intergruppal
Bristol scale "normal"	Secondary	Day 3	Shapiro-Wilk	Proportion	-	-	Fisher	Intergruppal
Saturation without supplemental O2	Secondary	Day 40	Shapiro-Wilk	Mean and SD	Unpaired T test	Mann Whitney	-	Intergruppal
Need for supplemental O2 at home	Secondary	Day 40	Shapiro-Wilk	Proportion	-	-	Fisher	Intergruppal
Days of supplemental O2 use at home	Secondary	Day 40	Shapiro-Wilk	Mean and SD	Unpaired T test	Mann Whitney	-	Intergruppal
Postcovid syndrome	Secondary	Day 40	Shapiro-Wilk	Proportion	-	-	Fisher	Intergruppal
Decrease in weight	Secondary	Day 40	Shapiro-Wilk	Proportion	-	-	Fisher	Intergruppal
Gastrointestinal symptoms	Secondary	Day 40	Shapiro-Wilk	Proportion	-	-	Fisher	Intergruppal

28. Missing data

Item 28: Missing data-reporting and assumptions/statistical methods to handle missing data

(multiple imputation)

Statistical methods to handle missing data will not be performed.

30. Harms

Item 30: Sufficient detail provided on summarizing harms

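### The 38 per group in SAP 11 and Protocol 8.3 comes from a one-proportion precision formula, so it gives no basis for the two-arm superiority comparison

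*SAP*

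**What the plan says.** SAP 11 and Protocol 8.3 give the same calculation, n = z²pq/e² with z = 1.96, p = 0.975, q = 0.025 and e = 0.05, "obtaining 38 patients per group for the sample". Neither says what p stands for. SAP 10 then draws numbers "until reaching 40 numbers per group", and SAP 20 speaks of 80 patients. Neither links 40 to 38.

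The conclusion is to be comparative. In SAP 12 the effect on survival and mortality "will be demonstrated by the significant superiority of IG over CG". SAP 27 states: "The analysis of the primary and secondary outcomes is shown in the following table". For overall survival that table names Kaplan-Meier and an intergroup log-rank test. Item 16 adds "P values will be one-sided". Item 18 sets confidence intervals at 95%, but the table names no between-arm survival estimate to which an interval would attach.

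Item 17 lists among its measures against type I error that "a specific sample size calculation will be performed". Item 26a calls three outcomes primary: overall mortality and survival, progression to ventilation ("Progression to AVM will be assessed from baseline until the last patient is intubated"), and mortality and survival in intubated patients. SAP 8 places the last two under secondary objectives.

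**The concern.** A sample size for a superiority trial should follow from a control rate, a difference or hazard ratio worth detecting, a significance level and a power. Here the only stated basis has one proportion and one margin of error. The words *per group* are attached to the result, but no second group enters the formula.

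Two things are at stake. A reader may take 38 for a powered superiority sample, which it is not. And because no other section states power, nobody can tell from the plan what mortality difference 40 per arm could detect, or how to read a non-significant log-rank result. With no between-arm estimate named in SAP 27, the precision of the difference would also go unstated. The same 38 is the only stated basis for the other two outcomes in Item 26a, one of which concerns intubated patients only.

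**Working it through.** **1. The plan's own figure.** Inputs from SAP 11: z = 1.96, p = 0.975, q = 0.025, e = 0.05.

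n = 1.96² × 0.975 × 0.025 / 0.05² = 3.8416 × 0.024375 / 0.0025 = 37.46, rounded up to 38. It reproduces.

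**2. What the ±5 points describe.** They are the 95% half-width for one group whose true proportion is 97.5%. Even if both arms had that proportion, the half-width for their difference at 38 per arm would be 1.96 × √(2 × 0.024375/38) = 7.0 points.

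**3. Precision and power at 40 per arm.** The plan gives no planning rates, so all rates below are assumptions. The 11.3% is the case fatality for Mexico (Protocol 2.2 and 4), and the 13.4% is the proportion of hospitalised patients who died (Protocol 3). The 20% and 25% rates and the cuts by one half and three quarters are chosen for illustration.

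- Half-width of the difference: 1.96 × √[(p₁q₁ + p₂q₂)/40]. Example, 11.3% v 5.65%: 1.96 × √[(0.1002 + 0.0533)/40] = 12.1 points. This is a Wald interval, rough with few deaths.
- Expected deaths: 40 × (p₁ + p₂).
- Power: log-rank simulation, exponential times, complete follow-up to day 40 from baseline, 40,000 runs, α = 0.05.

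| Control v IG mortality | Half-width (points) | Expected deaths | Power, one-sided / two-sided |
|---|---|---|---|
| 11.3% v 5.65% | ±12.1 | 6.8 | 25% / 15% |
| 11.3% v 2.825% | ±11.1 | 5.7 | 48% / 32% |
| 13.4% v 6.7% | ±13.1 | 8.0 | 27% / 17% |
| 13.4% v 3.35% | ±11.9 | 6.7 | 54% / 38% |
| 20% v 10% | ±15.5 | 12.0 | 35% / 24% |
| 20% v 5% | ±14.1 | 10.0 | 69% / 56% |
| 25% v 12.5% | ±16.9 | 15.0 | 42% / 30% |
| 25% v 6.25% | ±15.4 | 12.5 | 78% / 67% |

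Both sidednesses are shown because Item 16 is one-sided while the formula's 1.96 is a two-sided 95% value.

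**4. Checks on these figures.** With equal mortality of 5% to 20% in both arms, the simulated test size is 0.051 to 0.059 one-sided and 0.041 to 0.054 two-sided, so one-sided power is slightly flattered at low rates. Early loss lowers power: in a test case of 20% v 2.5%, an assumed 15% loss by day 40 takes power from about 87% / 77% to about 84% / 72%. Day 40 is counted from baseline, as in Items 15 and 26a; SAP 14 also ends each patient's study 40 days after discharge.

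**The case against.** **Forty per arm may be enough.** This stands as far as it goes. For an assumed 25% v 2.5%, simulated power is about 95% one-sided and 90% two-sided. A reader might infer from the low rows of the table that the trial is underpowered. The documents do not support that: the two background rates are a national case fatality and a general inpatient rate. They may be too low or too high for oxygen-requiring stage III patients from whom ventilated and ICU cases are excluded. The fault is that no scenario is stated.

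**Other readings that go too far.** The step from 38 to 40 could be read as a shortfall, but 40 exceeds 38, so it is only unexplained. A reader might also notice that p = 0.975 equals the IG survival reported with SAP Figure 2 (one death in 40) and infer that p came from the results. Neither document says where p came from, so nothing follows from the match.

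**The reported log-rank p = 0.027 settles the matter.** It does not. An observed result supplies no design basis.

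**The orientation rates are a reviewer's choices.** True, and the formula point needs none of them. They should be printed only as labelled assumptions, with the caveats on loss and test size.

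**One wording cannot serve both documents.** This stands. The Protocol's objective is complications. Its follow-up is at most 21 days and ends at discharge or ICU access. It has no log-rank test, no day-40 endpoint and no Item 26a.

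**Nothing can change now.** The SAP already carries results to April 2021, so the sample size is fixed. The description of its basis and the reporting of the survival difference can still be corrected.

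**Conclusion.** The stated basis for the trial size is wrong as written and must be corrected. The sum is sound, but the formula answers a different question from the one that SAP 12 and SAP 27 ask. This conclusion rests on the text alone and needs no assumed rate.

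The size of the gap does depend on assumptions. With control mortality of 11.3% to 25% cut by one half to three quarters, and complete follow-up, the half-width for the difference at 40 per arm is about ±11 to ±17 points, against the ±5 in the formula. Over the same scenarios log-rank power runs from about 25% to 78% one-sided and from about 15% to 67% two-sided. That spread shows how much the missing inputs matter. It is not evidence that 40 per arm is inadequate.

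**What to change.** **SAP 11.** Keep the formula as the record of how 38 was obtained and add a dated clarification:

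> This formula gives the precision of a single proportion. No power was specified for the overall survival comparison, or for progression to ventilation and survival in intubated patients (primary in Item 26a, secondary in SAP 8; to be reconciled). Forty per arm are randomised [state how this relates to 38]. For orientation only, with assumed day-40 mortality, complete follow-up to day 40 from baseline and log-rank simulation at 40 per arm, power (one-sided / two-sided 0.05) is about 25-54% / 15-38% for control mortality of 11.3-13.4% reduced by one half to three quarters, and about 35-78% / 24-67% for 20-25% with the same reductions. Loss to follow-up lowers these figures, and the one-sided figures are slightly flattered because the simulated one-sided size reaches about 0.059 at low event rates.

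Leave the 20% v 2.5% case out of this text, since it lies close to the reported 17.5% v 2.5% (7/40 v 1/40). Do not use the results in the SAP's closing tables and figure legends as planning inputs. If a power calculation made before enrolment exists, give it with its inputs instead.

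**SAP 18 and 27.** Report the day-40 overall survival difference (IG minus CG) with its 95% confidence interval, and state that a non-significant result will not be read as no effect.

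**Protocol 8.3.** State only that the formula gives the precision of one proportion and that no power was specified for the between-group comparison of complications, and cross-refer to SAP 11 for survival.

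**Cost.** Wording only, with no extra patients or data. The stated basis for the trial size becomes less favourable, and the orientation figures must be revised if the sidedness in Item 16 changes.
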